#### 7.7.1. Prior Medication

Prior medications will be defined as medications that stop before Trial Day 1. Prior

## Statistical Analysis Plan

medications will be flagged on the concomitant medication listing.

The number and percentage of subjects with prior medications will be summarized for the ITT set by anatomical main group, therapeutic subgroup and preferred drug name.

### 7.7.2. Screening Medication

Screening medications will be defined as any medications that were started prior to the screening visit and were ongoing at the time of screening, or any that were started on the day of the screening visit, or stopped on the day of the screening visit. Screening medications will be flagged on the concomitant medication listing.

The number and percentage of subjects with screening medications will be summarized by anatomical main group, therapeutic subgroup and preferred drug name for the ITT set and for the subset of the MTT set who did not go on to be randomized.

### 7.7.3. Concomitant Medication

Concomitant medications taken during the follow-up phase will be defined as any medications that were taken on or after Trial Day 1. All concomitant therapies will be listed.

The number and percentage of subjects with concomitant medications during the follow-up phase will be summarized for the ITT and SAF sets by anatomical main group, therapeutic subgroup and preferred drug name. In addition, separate summaries will be presented for the ITT set for the number and percentage of subjects with the following categories of concomitant medications by anatomical main group, therapeutic subgroup and preferred drug name:

- Maintained medications - defined as concomitant medications started before Trial Day 1.
- New medications during trial medication - defined as concomitant medications started on or after Treatment Day 1 and before or on date of last trial medication.
- New medications whilst off trial medication - defined as concomitant medications started after last date of trial medication or started on or after Trial Day 1 and before first dose of trial medication.

[figure not shown]
All concomitant medications recorded should fall into one of the above categories.

Pharmaxis Ltd

DPM-CF-303

Final v1.0

## Statistical Analysis Plan

### 7.7.4. Antibiotic Use

Concomitant antibiotic use due to PDPE and PE will be summarized for the ITT set by preferred drug name. These medications will be identified as detailed in Section 4.2.1.

## Statistical Analysis Plan

### 8. EFFICACY

The hypotheses for the primary efficacy endpoint and the key secondary efficacy endpoints will be formally tested using a hierarchical testing approach to preserve the Type 1 error rate. Objectives will be tested in the order in which they are ranked in Section 4. Analysis of hierarchical secondary objectives will continue until a non-significant p-value (i.e.  $p > 0.05$ ) is returned.

All efficacy analyses will be performed on the ITT set unless otherwise specified.

#### 8.1. PRIMARY EFFICACY ENDPOINT AND ANALYSIS

The primary endpoint is the absolute change from baseline FEV1 (L) over the 26-week treatment period (measured at Weeks 6, 14 and 26). The primary analysis will include assessments as specified up until the time of last participation for each subject, including those performed off trial medication. For subjects who have an IMP discontinuation visit, the spirometry assessment done at this visit can be used instead of the assessment performed at the scheduled visit in line with the rules defined in Section 6.4.

In order to assess the potential impact of missing data on the results, sensitivity analyses will be performed (see Section 8.1.2 for more details):

- Pattern Mixture Model.
- Tipping Point Analysis.
- Mixed model repeated measures (MMRM) without imputation.
- Responder Analysis.

The following supportive analyses will also be performed:

- Using the PP set.
- Absolute change from baseline FEV1 (L) at 26 weeks and at 6 and 14 weeks.
- Absolute change from baseline percent predicted FEV1 (%) over 26 weeks.
- Relative change from baseline FEV1 (L) over 26 weeks.
- Relative change from baseline percent predicted FEV1 (%) over 26 weeks.

In addition, the following supportive analyses on the absolute change from baseline FEV1 (L) over the 26 week treatment period will be conducted based on on-treatment period data only:

Pharmaxis Ltd

DPM-CF-303

Final v1.0

## Statistical Analysis Plan

- MMRM with BOCF+IUDR imputation.
- Pattern mixture model.
- MMRM without BOCF.

The primary analysis of absolute change in FEV1 over the 26 week treatment period and the supportive analysis of relative change in FEV1 over the 26 week treatment period will be repeated by the subgroups specified in Section 6.6 on the ITT set only.

The results from the primary analysis, the sensitivity analyses, the supportive analyses, and the subgroup analyses for the primary endpoint will be presented in forest plots to graphically explore the consistency of the estimated treatment effect.

### 8.1.1. Primary Analysis of the Primary Endpoint

#### Descriptive Summaries:

FEV1 (L) absolute change from baseline and relative change from baseline (% change) and percent predicted FEV1 (%) absolute change from baseline and relative change from baseline (% change) will be summarized by visit using summary statistics for continuous variables. Two summaries will be produced based on actual data and imputed missing data as described below. All these summaries will be performed on the ITT and PP sets. In addition, FEV1 (L) absolute change from baseline and relative change from baseline (% change) will be summarized for on trial medication data only (i.e. excluding data >7 days after trial medication stop date), by visit, using summary statistics for continuous variables, based both on actual data and imputed missing data, for the ITT set.

#### Primary Analysis Method:

The mean absolute change from baseline FEV1 (L) over 26 weeks (including assessments at Weeks 6, 14 and 26) will be compared between the two treatment groups with a restricted maximum likelihood (REML) based MMRM approach.

The model will include the fixed, categorical effects of treatment group, rhDNase use, pooled country, visit, and treatment group-by-visit interaction, as well as the continuous, fixed covariate of baseline FEV1 and also disease severity (percent predicted FEV1 at baseline). Subject will be included in the model as a random effect. An unstructured (co)variance structure will be used to model the within-subject errors. The Kenward-Roger approximation will be used to estimate denominator degrees of freedom.

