10 STATISTICAL METHODS

10.1 General considerations

A full description of the statistical methods planned for this trial can be found in the DPM-CF-303 Statistical Analysis Plan (SAP).

Efficacy analyses will be conducted using the intention to treat (ITT) analysis set (refer **Section 10.1.2.1**) as well as the per protocol (PP) analysis set (refer **Section 10.1.2.2**). Safety analyses will be conducted on the safety analysis set (refer **Section 10.1.2.3**).

Significance tests will be performed assuming a two-sided 0.05 significance level; two-sided 95% confidence intervals will also be computed.

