10.1.1 Sample size justification

Enrolment will continue until at least 350 subjects have been randomized to treatment in a 1:1 ratio.

Assuming that the change from baseline in FEV₁ on control is 0 mL and the change from baseline in FEV₁ on mannitol is 80 mL, then a sample size of 350 (175 Mannitol : 175 Control) subjects will yield 90 % power at the 0.05 significance level to detect this difference between the treatment groups assuming a pooled standard deviation of 230 mL. The sample size calculation is based on a t-test of the treatment contrast at week 26. While this approach is not completely concordant with the primary analysis which computes the mean change in FEV₁ over all three post-baseline visits it can be considered a suitable method for estimating sample sizes for longitudinal analyses and is likely to be conservative.

The estimated pooled standard deviation of 230 mL is based on the observed pooled standard deviation in the pooled adult DPM-CF-301 and DPM-CF-302 data from subjects who completed the studies.

This minimum sample size is based upon the observed pooled standard deviation from both DPM-CF-301 and DPM-CF-302 studies in subjects with baseline FEV₁ of more than 40% but less than 90%. However the observed standard deviations were different in these two

previous studies, and were highly influenced by a few outlying values. In addition, the present trial (DPM-CF-303) will be conducted at different sites and in different countries to the previous studies. Thus there is some uncertainty as to what the observed standard deviation is likely to be in this trial (DPM-CF-303). For these reasons a sample size re-estimation is planned to be completed after at least 300 subjects have been recruited and will be based on all available 26-week data. This blinded sample size re-estimation will be based on the method of Kieser and Friede [15] which preserves the overall type 1 error rate. Therefore no adjustments to the overall significance level for the trial is required. See Section 10.1.5 for more information.

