### 6.2.4. Baseline

The baseline value for all efficacy endpoints will be taken as Visit 1. It will be assumed that assessments performed on this visit were prior to first trial medication administration, with the exception of post-dose spirometry. Therefore, efficacy baseline will be the Visit 1 measurement unless the Visit 1 measurement is missing, where the Visit 0 measurement will be used as baseline.

The baseline value for safety endpoints (vital signs and physical examination) will be taken as the latest available measurement prior to or on Treatment Day 1 (i.e. day of first trial medication dose). It will be assumed that safety assessments performed on Treatment Day 1 were prior to trial medication administration. Baseline will be the Visit 1 measurement.

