## Statistical Analysis Plan

missing FEV1 values at post-baseline visits will be imputed using multiple imputation (MI) from the distribution of baseline values, using the method of Ratitch et al for pattern imputation based on reasons for dropout.

This approach is in line with the one defined for the primary endpoint analysis, where subjects withdrawing from the trial for AE, death, physician decision or lack of efficacy are considered to stop benefiting from the trial medication and return to their baseline status (i.e. BOCF approach; see GRP2 imputation model below), while for subjects withdrawing from the trial for other reasons, it is assumed that they would have continued to benefit from the trial medication in line with subjects completing the trial (see GRP4 and GRP6 imputation models below).

In a preliminary step, imputation based on the missing at random (MAR) assumption will be performed using the joint modeling approach in order to obtain monotone missing data patterns. The imputation model will include the following variables: treatment group, rhDNase use, pooled country, FEV1 (L) from Visit 0 to Visit 4.

Then, a regression-based imputation will be performed for the remaining missing FEV1 values. The strategy for imputation will be based on the definition of the following groups of observed data and patterns of missingness:

(GRP1) Subjects from both treatment groups with non-missing baseline FEV1 values

(GRP2) Subjects from both treatment groups who withdraw from the trial due to AE, death, physician decision, or lack of efficacy

(GRP3) Subjects in the control group who completed the trial

(GRP4) Subjects in the control group who withdraw from the trial because of other reasons

(GRP5) Subjects in the mannitol group who completed the trial

(GRP6) Subjects in the mannitol group who withdraw from the trial because of other reasons

Imputation will be performed:

- In pattern (GRP2) using a model for baseline FEV1 including rhDNase use, pooled country and FEV1 (L) at Visit 0, estimated on the (GRP1) group.
- In pattern (GRP4) using a model including rhDNase use, pooled country, FEV1 (L) from Visit 0 to Visit 4, estimated on the (GRP3) group.

Pharmaxis Ltd

DPM-CF-303

Final v1.0

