## Statistical Analysis Plan

imputed). It is assumed that a MAR missingness pattern is the most probable in this context.

8. Protocolled primary sensitivity analyses #1 remains unchanged but has become primary sensitivity analysis #3. It will be performed to elicit insights into the effect of imputation via the planned BOCF+IUDR framework and the primary analyses will be repeated without imputation of missing post-baseline FEV1.
9. Protocolled primary sensitivity analyses #2, #3, #5, #7, and #9 have been removed to provide a more targeted and focused set of analyses to test the robustness of the primary results to varying assumptions (Section 8.1).
  - a. Protocolled primary sensitivity analysis #2 was to elicit insights into the effects of including data from subjects after cessation of trial treatment and the primary analyses was to be repeated excluding these data both with imputation of missing post-baseline FEV1 assessments and without imputation. These analyses will now be included as supportive analyses (Supportive analyses 6 and 8).
  - b. Protocolled primary sensitivity analysis #3 was sensitivity of the primary result to choice of “across Weeks 6 to 26” versus “at Week 26” estimates of the treatment effect, gauged by computing the LS mean treatment group difference at Week 26; this result will be presented as part of the primary endpoint primary analysis and is now included as a supportive analysis (Supportive analysis 2).
  - c. Protocolled primary sensitivity analysis #5 was to determine if the primary results are sensitive to any observed changes between screening and Visit 1 in FEV1, and the primary analysis was to be repeated using the mean FEV1 measurement from screening (Visit 0) and Visit 1.
  - d. Protocolled primary sensitivity analysis #7 was a responder analysis where the cut-off for classification as a responder was to be change from baseline FEV1 greater than: -300, -250, -200, -150, -100, -50, 0, 50, 100, 150, 200, 250, and 300 mL respectively.
  - e. Protocolled primary sensitivity analysis #9 was to explore the effect of different imputation methods, the primary analysis was to be repeated using a worst observation carried forward+IUDR method rather than the BOCF+IUDR framework.
10. Primary sensitivity analysis #4 has become primary sensitivity analysis #1 and has been changed to use the Ratitch method (Section 8.1.2). The intention of this

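### The primary FEV1 model leaves out the Visit 0 reading already collected; adding it as a separate covariate would gain precision at almost no cost

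*SAP*

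**What the plan says.** Spirometry is done at Visit 0, before the premedication and mannitol tolerance test (Protocol 8.1.1 and 8.1.1.1). It is repeated before dosing at Visit 1, normally 2 to 5 weeks later (Protocol 8.1.2.1). Protocol 8.2.1.1 puts spirometry ahead of any bronchodilator.

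SAP 6.2.4 says "efficacy baseline will be the Visit 1 measurement unless the Visit 1 measurement is missing"; only then does Visit 0 stand in. The primary MMRM (SAP 8.1.1) adjusts for "the continuous, fixed covariate of baseline FEV 1 and also disease severity", the latter being percent predicted FEV1 at baseline. By the formula in SAP 4.1, percent predicted is that same FEV1 divided by a value predicted from age, height, sex and race.

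Protocol 10.2.5.5 planned a repeat of the primary analysis with the mean of the two visits as baseline. SAP Section 11, item 9, removes it and describes its purpose: "Protocolled primary sensitivity analysis #5 was to determine if the primary results are sensitive to any observed changes between screening and Visit 1". Analyses #2 and #3, removed under the same item, return as supportive analyses. #5 does not.

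Visit 0 is still used in SAP 8.1.2. For the imputation step of Sensitivity Analysis 1, "The imputation model will include the following variables: treatment group, rhDNase use, pooled country", and the list goes on to FEV1 at every visit starting with Visit 0. Sensitivity Analysis 2 uses the same list. The ANCOVA fitted to the imputed data does not include Visit 0.

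**The concern.** One baseline reading carries its whole measurement and day-to-day error into every change score. Adjusting for that same reading removes part of the damage. Percent predicted FEV1 adds information on age, height, sex and race, but no second reading of lung function. A second untreated reading would give a better estimate of where the subject started, and the trial has already paid for it. The SAP treats it as predictive when imputing missing FEV1, then leaves it out of the treatment comparison.

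At stake is the width of the interval around the FEV1 difference, and the same for FVC, the first hierarchical secondary endpoint. This matters more here than in many trials. The re-estimation raised the target to 440 (SAP Section 10), the maximum in Protocol Table 7, and 423 subjects were randomised. Protocol 2.3 also regards improvements smaller than the 80 mL design value as meaningful.

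**Working it through.** **1. The plan's own figure.** Protocol 10.1 and 10.1.1 give: "Significance tests will be performed assuming a two-sided 0.05 significance level"; the change "on mannitol is 80 mL" against 0 mL on control; "assuming a pooled standard deviation of 230 mL"; and 175 per arm, which "will yield 90 % power at the 0.05 significance level".

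n per arm = 2(1.960 + 1.282)² × (230/80)² = 173.7, so 174 per arm and 348 in total, against 350 stated. Power at 175 per arm is 90.2% (normal) or 90.1% (noncentral t). The figure reproduces. It is a Week 26 t-test and takes no credit for covariates.

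**2. Model for the gain.** FEV1 at time t = subject level + drift(t) + independent visit noise.
- From the plan: Var(Week 26 − Visit 1) = 230² mL².
- Assumed, not in the documents: a share s of that variance is noise, so each visit has noise variance s × 230²/2, and drift from Visit 1 to Week 26 has variance (1 − s) × 230². The between-subject SD is 600 to 800 mL. Visit 0 is 3.5 weeks before Visit 1. Data are complete and multivariate normal.
- Four drift structures: random slope, random walk, correlation decaying exponentially over 8 weeks, and a persistent step after Visit 1.

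The quantity compared is the residual variance of the mean of Weeks 6, 14 and 26, given Visit 1 alone and given Visits 0 and 1.

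**3. Upper limit by hand.** With noise only and a very large between-subject SD, the residual variance is σ²(1/3 + 1) with one baseline and σ²(1/3 + 1/2) with two. The cut is 1 − (5/6)/(4/3) = 37.5%. With σ² = 230²/2 = 26,450, the SDs are 188 and 148 mL.

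**4. Variance cut from adding Visit 0** (ranges cover between-subject SD 600 to 800 mL):

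| Noise share s | Random slope | Random walk | 8-week decay | Persistent step |
|---|---|---|---|---|
| 100% | 35.5–36.4% | 35.5–36.4% | 35.5–36.4% | 35.5–36.4% |
| 75% | 27.0–27.6% | 28.1–28.8% | 29.8–30.6% | 23.7–24.2% |
| 50% | 16.3–16.6% | 19.3–19.7% | 23.5–24.2% | 14.4–14.6% |
| 25% | 3.6–3.7% | 8.9–9.1% | 16.7–17.2% | 6.7% |
| 10% | 1.1% | 2.5% | 12.3–12.8% | 2.6% |

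A compound-symmetry check with no drift gives 28% at visit-to-visit correlation 0.7, 35% at 0.9 and 37% at 0.99.

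**5. Interval width.** A variance cut r narrows the interval by 1 − √(1 − r). For r = 14.4% that is 7.5%, for 24.2% it is 12.9%, and for 36% it is 20%.

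**6. Power.** SE = 2 × SD/√N, and power = Φ(difference/SE − 1.96).
- 80 mL, N = 350, all noise: residual SD falls from 183–185 to 147–148 mL; power rises from about 98% to 99.9%.
- 80 mL, N = 350, lowest-power case (10% noise, persistent step): SD falls from 226.1 to 223.2 mL; power goes from 91.1% to 91.8%.
- Smaller effect, as an illustration: 54.1 mL (the all-ages result of the second earlier trial, Protocol Table 1), N = 423, change SD 250 mL (just above the top cut-off in Table 7), half noise. Power rises from 69–88% to 75–93% across the four structures, a gain of about 5 to 9 points in each.

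**7. Averaging instead.** Using the mean of the two visits gives nearly the same gain when noise dominates. At 10% noise it increases the variance by about 13% under a random slope and 1% under a random walk. The separate covariate lost no precision in any scenario run.

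**The case against.** The planned model is valid. Adjusting for the pre-dose baseline is standard, and the SAP already improves on the protocol by adding baseline FEV1 (Section 11, item 5). The noise share and the between-subject SD are unknown. Protocol 10.1.1 says a few outlying values strongly influenced the earlier SDs, which fits poorly with a homogeneous normal model. At 80 mL, power is at least 91% without the change in every scenario. All of this stands, and it limits the point to precision.

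It also stands that Visit 0 is not a clean replicate. It is the eligibility visit. The check that withholding periods were kept, with postponement if they were not, is written for Visits 1 to 4 only. The requirement to be free of exacerbation attaches to Visit 1, and an exacerbation after screening lengthens the gap (Protocol 6.1). On hypertonic saline, Protocol 6.2.4 bars maintenance use from Visit 0, while 5.3 and 8.1.2.1 tie the washout to Visit 1 and SAP 7.3 tabulates use at screening. Those passages should be reconciled. These differences argue against averaging the visits. They do not argue against a covariate whose weight is estimated from the data.

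A reader might infer that the treatment estimate is biased, or that 350 subjects were too few. Neither follows: randomisation balances the baseline noise between arms, and the sample size assumes no covariate gain. A reader might also infer that dropping #5 removed a precision analysis. Its stated purpose was to test for shifts between screening and baseline, and the removal is declared with a reason. Nor is Visit 0 wholly unused, since it informs two imputation models.

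**Conclusion.** The point holds as a loss of precision that can be avoided. The primary comparison uses one of two untreated FEV1 readings, and no analysis left in the SAP uses both as baseline or as covariates. The gain from adding Visit 0 lies between about 1% and 36% of the residual variance: 14% to 24% if half of the change variance is noise, and 4% to 17% if a quarter is. These figures rest on the assumed noise share, drift structure and between-subject SD. They ignore missing data and the baseline-carried-forward imputation, and take one fixed gap between the visits. Type I error, estimand and planned N are unaffected. The practical benefit is a narrower interval for FEV1 and FVC, and better power if the true effect is below 80 mL.

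**What to change.** Before unblinding:

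- In SAP 8.1.1, add Visit 0 pre-bronchodilator FEV1 as a continuous fixed covariate beside Visit 1 FEV1. Keep change from Visit 1 as the outcome. Do the same with Visit 0 FVC in 8.2.1.
- State that where Visit 1 is missing and Visit 0 serves as baseline, both covariates take the Visit 0 value. Give a matching rule for a missing Visit 0 so that no subject drops out of the model.
- Carry the covariate into the ANCOVAs of Sensitivity Analyses 1 and 2, and record the change in Section 11.
- Optionally, restore protocol sensitivity analysis #5, but only as a robustness check on screening-to-baseline change.

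The cost is a few lines of SAP text and programming and one degree of freedom per model. No new data are needed, and Visit 0 FEV1 should be nearly complete because eligibility depends on it.

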## Statistical Analysis Plan

[REDACTED]

Least squares means (LS means) and mean treatment group difference, standard error (SE), 95% CIs, and p-value for the treatment group effect averaged across the trial, with the same weight applied to each visit, will be presented.

Plots of the LS means (95% CI) for the primary endpoint against visit will be presented for the ITT and PP sets, highlighting significant differences between the treatment groups at any timepoint.

